10. STUDY CALENDAR

Screening evaluations are to be conducted within 3 weeks prior to study registration. Procedures done within a week of study registration don't need to be repeated to establish baseline. Scans and x-rays must be done \leq 4 weeks prior to study registration. In an event that the participant's condition is deteriorating, laboratory evaluations should be repeated within 48 hours prior to initiation of the next cycle of therapy. Each treatment cycle in this study is 28 days long.

Assessments must be performed prior to administration of any study agent. Study assessments and agents should be administered within \pm 3 days of the protocol-specified date, unless otherwise noted.

Studies	Screening	Enrollment	Treatment phase				End of Treatment ^h	Follow up visit 30 days after the last dose ^h	Survival Follow up
			Cycle 1	Cycle 2	Cycle 3	Cycle 4			
			Day	Day	Day	Day			
Informed consent	X								
Medical History	X								
Physical exam (Ht, Wt, VS, PS)	X		X	X	X	X	X	X	
Routine labs ^b	X		X	X	X	X	X	X	
B-HCG (WOCBP only) ^c	X		X	X	X	X	X	X	
FSH test ^d	X								
ECG	X						X		

Photographs, measurements ^e	X		X	X	X	X		X ^h	X ^h
Biopsy samples ^f	X							X	X ^h
Correlative biopsies ^f	X							X	X ^h
Correlative blood			X	X	X	X		X	
Nivolumab			X	X	X	X			
Quality of life survey ^g	X				X		X	X	
Adverse event evaluation			X	X	X	X	X	X	
Survival Status									X ^h

- a) Physical exam is symptom directed. Height measured at screening only.
- b) Routine labs include: CBC with differential, LFTs, chemistries, TSH, phosphorous. Baseline HCV antibody, hepatitis B surface antigen, hepatitis B surface antibody, and hepatitis B core antibody testing is required at screening only.
- c) Serum or urine within 24 hours prior to first dose.
- d) Follicle Stimulating Hormone test will be performed only on women who are under 55 years of age.
- e) Color digital photographs capturing all oral precancerous sites but including the entire oral cavity (any site biopsied should be photographed). Bidimensional measurements of each oral precancerous lesion should be obtained and recorded, using the largest maximum diameter of each site.
- f) Baseline biopsy can be performed any time after the subject has consented up until C1D1. Archival tissue is not acceptable. Fresh biopsy is mandatory (at up to three sites per patient). Fresh tissue is also collected following completion of treatment. Biopsy will also be recommended if the patient progresses to invasive squamous cell carcinoma of the head and neck. Fresh tissue may also be collected at time of progression.
- g) Quality of life surveys will be completed at screening, after 2 cycles of treatment, at the end of treatment, and at 30-day follow-up. Patients will complete the chronic oral mucosal diseases quality of life questionnaire (COMD QLQ [66]). This is a validated instrument that assesses various aspects of oral health and function that has been shown to perform well in patients with oral mucosal diseases, including oral precancerous conditions. *See Appendix C* for the full questionnaire.
- h) Participants, regardless if they receive the full course of prescribed therapy, will be followed for best overall response and development of first invasive OSCC every cycle during treatment (including a survival status update). Post end-of-protocol treatment, if first invasive OSCC has not been confirmed, assessments will continue every 3-6 months until best overall response and first invasive OSCC are documented (with survival status updates during this time period as well). After documentation of first invasive OSCC, survival status will continue to be updated every 3 months until death or 5 years from study registration (whichever occurs first). Photographs and measurements may continue at PI discretion after first invasive OSCC and during survival follow up. Clinically indicated biopsies that occur at or following first invasive OSCC can be used for study correlatives at PI discretion during survival follow up.

11. MEASUREMENT OF EFFECT

11.1 Measurement of Effect – OPVL lesions

For the purposes of this study, participants will be re-evaluated for change in the measurements of each oral leukoplakia site at every study visit following initial study drug dosing. In addition, re-biopsy of initial oral leukoplakia sites (up to 3 per patient) will be obtained at the end of treatment, and to development of invasive oral cancer up to 5 years from study registration. Timelines are described in *Section 10*.

Response will be measured by: (1) measuring the change in size of each oral leukoplakia lesion,

and (2) by assessing histopathological change (a change in the degree of dysplasia as defined by histologic features) [modified from Wan der Waal I, et al. *Oral Oncol* 2000; 36(3):264-6]. *See Response Criteria below.*

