1. OBJECTIVES

1.1 Study Design

This is a phase II, open label, non-randomized, trial of nivolumab (anti-PD-1) in patients with high-risk oral (precancerous) lesions, specifically oral proliferative verrucous leukoplakia (PVL), leukoplakia with moderate dysplasia, and erythroleukoplakic lesions. Following initial biopsy of up to 3 sites per patient, four monthly doses of the nivolumab will be given. Patients will be followed for evidence of clinical regression (in bidimensional measurement) of lesions. After treatment, patients will undergo re-biopsy of the same leukoplakia site(s) which will be evaluated for regression of the degree of dysplasia (if applicable). The primary endpoint of the study is to evaluate the best overall response rate to nivolumab in high-risk oral leukoplakia patients. Secondary endpoints will include safety, toxicity assessments, quality of life scores, time to next head & neck cancer surgery, cancer-free survival (CFS), overall survival (OS) , and genomic and immune correlates of response.

We hypothesize that nivolumab will cause regression in both the size and the degree of dysplasia of high-risk oral precancerous lesions, leading to a longer time to the next head & neck surgery, as well as improved quality of life and improved survival.

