The specimen must arrive in a timely fashion to facilitate processing for evaluation of immune cells. Blood must be spun within 3 hours of collection for 15 min at 3000 rpm. The plasma is then aliquoted into 2 x 60 μ L aliquots and immediately frozen at -80°C. Plasma is thawed on ice prior to usage. 50 μ L of plasma is sufficient for each assay, where triplicate measurements per sample per time point are envisaged. Plasma is diluted 1:4 (15 μ L in 50 μ L reaction) prior to transfer to plate-based assay. We will utilize a multiplex magnetic bead-based sandwich ELISA assay to simultaneously measure the soluble form of 14 immune checkpoint molecules (BTLA, CTLA-4, PD-1, PD-L1, PD-L2, GITR, HVEM, IDO, LAG-3, TIM-3, CD27, CD28, CD80 and CD137). Each bead is encoded with a ratiometric concentration of 2 IR dyes and act as a barcode, unique to each protein. The final detection complex is formed with the addition of streptavidin-phycoerythrin (SA-PE) conjugate, where the phycoerythrin serves as the fluorescent reporter. Plasma concentration levels, measured in pg/mL, for each protein are derived from 5-parameter curve fitting models. Fold change relative to pre-treated baseline are calculated and plotted as log2FC to establish biological significance. The changes in secretion levels will be correlated with tumor immune parameters and clinical response.

Immunohistochemistry

At the time of pre- and post-treatment biopsy, one core of fresh tissue will be allocated to a standard orange-top specimen cup containing 10% neutral buffered formalin. The specimen will be labeled with the participant's initials, medical record number and the date of acquisition. After collection, the specimen will be sent to the Brigham & Women's Hospital (BWH) pathology division for processing. Following standard tissue processing, sectioning and slide preparation for histopathologic review, the specimen will be stored in accordance with BWH protocols (both tissue blocks and tissue slides). At a later time, we will then request tissue block retrieval through the Pathology Specimen Locator Core with preparation of 5 unstained slides through the Specialized Histopathology (SHP) Core service at BWH. SHP will then prepare 1 stained

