11.1.4 Response Criteria

11.1.4.1 Evaluation of Target Lesions

STEP 1: Grade each individual lesion by size and histology to achieve the individual score of each site (up to 3 per patient).

Size	Criteria
L1	A lesion measuring < 2 cm in largest diameter
L2	A lesion measuring 2-3 cm in largest diameter
L3	A lesion measuring > 3 cm in largest diameter

Histology Criteria

P0 Keratosis of unknown significance with or without mild atypia (hyperkeratosis should not be reactive, such as from friction or factitial injury)

P1 Mild dysplasia

P2 Moderate dysplasia

P3 Severe dysplasia

Examples:

Patient A has 3 sites (1 cm, mild dysplasia = L1P1; 2.5 cm, mild dysplasia = L2P1; 2 cm, severe dysplasia = L2P3)

Patient B has 1 site (4 cm, moderate dysplasia = L3P2)

STEP 2: Score the patients individual sites using the below grid. A higher score reflects more advanced disease.

Points	Composite of Size / Histology
2	L1 P0
4	L1 P1
6	L1 P2
8	L1 P3
12	L2 P0
14	L2 P1
16	L2 P2

18	L2 P3
22	L3 P0
24	L3 P1
26	L3 P2
28	L3 P3

Examples:

Patient A has 3 sites (L1P1 = 4; L2P1 = 16; L2P3 = 18; total points = 38 is the composite score)

Patient B has 1 site (L3P2 = 26; total points = 26 is the composite score)

STEP 3: Following nivolumab, repeat measurements and histologic assessments. Recalculate the above score for each patient to assess the change in the composite score. Then calculate the change over the total baseline composite score as a (%) to the first decimal place.

Examples:

Patient A has 3 sites now (1 cm, mild dysplasia = L1P1; 2 cm, no dysplasia = L2P0; 1 cm, mild dysplasia = L1P1)

Patient B has 1 site now (2 cm, moderate dysplasia = L2P2)

Patient A has 3 sites now (L1P1 = 4; L2P0 = 12; L1P1 = 4; total points = 20 is the new composite score)

Patient B has 1 site now (L2P2 = 16; total points = 16 is the new composite score)

Patient A has 3 sites ($38 - 20$ points = $\Delta 18$), $18/38 = 47.4\%$

Patient B has 1 site ($26 - 16$ points = $\Delta 10$), $10/26 = 38.5\%$

STEP 4: Using the difference in the composite score for each patient, match to the response grid below.

Definition Best Overall Response

A decrease of > 80% or more CR

A decrease of 40-80% PR

Neither PR or PD SD

An increase of 10% or more PD

Examples:

Patient A has 3 sites ($38 - 20$ points = $\Delta 18$), $18/38 = 47.4\%$, called PR

Patient B has 1 site ($26 - 16$ points = $\Delta 10$), $10/26 = 38.5\%$, called SD

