Complete Response (CR): A decrease of >80% in the total composite score, for at least 4 weeks.

Partial Response (PR): A decrease of 40-80% in the total composite score.

Progressive Disease (PD): At least a 10% increase in the total composite score.

(Note: the appearance of one or more new lesions is also considered progression).

Stable Disease (SD): Neither sufficient shrinkage to qualify for PR nor sufficient increase to qualify for PD.

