11.1.4.4 Evaluation of Best Overall Response

The best overall response is the best response recorded from study registration until first disease progression/diagnosis of invasive OSCC (taking as reference for progressive disease the smallest measurements recorded since the treatment started). The patient's best response assignment will depend on the achievement of both measurement and histologic criteria.

Measurable Disease (*i.e.*, Target Disease)

Target Lesions	Non-Target Lesions	New Lesions	Overall Response	Best Overall Response when Confirmation is Required*
CR	CR	No	CR	≥ 4 wks Confirmation**
CR	Non-CR/Non-PD	No	PR	≥ 4 wks Confirmation**
CR	Not evaluated	No	PR	
PR	Non-CR/Non-PD/not	No	PR	

	evaluated				
SD	Non-CR/Non-PD/not evaluated	No	SD	Documented at least once \geq 4 weeks from baseline**	
PD	Any	Yes or No	PD	no prior SD, PR or CR	
Any	PD***	Yes or No	PD		
Any	Any	Yes	PD		

* See manuscript for further details on what is evidence of a new lesion.
 
** Only for non-randomized trials with response as primary endpoint.
 
*** In exceptional circumstances, unequivocal progression in non-target lesions may be accepted as disease progression.
					

Note: Participants with a global deterioration of health status requiring discontinuation of treatment without objective evidence of disease progression at that time should be reported as “symptomatic deterioration.” Every effort should be made to document the objective progression even after discontinuation of treatment.
					

Non-Measurable Disease (*i.e.*, Non-Target Disease)

Non-Target Lesions	New Lesions	Overall Response
CR	No	CR
Non-CR/non-PD	No	Non-CR/non-PD*
Not all evaluated	No	Not evaluated
Unequivocal PD	Yes or No	PD
Any	Yes	PD

* ‘Non-CR/non-PD’ is preferred over ‘stable disease’ for non-target disease since SD is increasingly used as an endpoint for assessment of efficacy in some trials so to assign this category when no lesions can be measured is not advised.

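### Dysplasia grade feeds the primary response score, but the plan does not mask the grader to time point, and one grade can move a case across the 40% response cut-off.

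*Combined protocol and SAP*

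**What the plan says.** Section 1.1 describes the design: "This is a phase II, open label, non-randomized, trial of nivolumab (anti-PD-1"). Section 11.1 gives response two components, change in lesion size and histology, the second assessed "by assessing histopathological change (a change in the degree of dysplasia as defined by histologic features"). Section 11.1.4.4 adds that the "best response assignment will depend on the achievement of both measurement and histologic criteria".

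Section 11.1.4.1 turns this into a score. Each of up to three sites gets a size class (L1 to L3) and a histology grade (P0 to P3), and a printed grid converts the pair to points: "A higher score reflects more advanced disease". Step 3 repeats the exercise after treatment: "Following nivolumab, repeat measurements and histologic assessments". Partial response (PR) is "A decrease of 40-80% in the total composite score"; progression is "At least a 10% increase in the total composite score".

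Section 13 counts complete and partial responses. Accrual stops if 1 or fewer of the first 16 patients respond, and the regimen is considered for further testing if more than 5 of 33 respond.

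On who reads the slides, the plan says little:

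- Section 9.1 gives an oral pathologist the scoring of immune stains. It does not mention dysplasia grading for the endpoint.
- The review panel in Section 11.1.4.2 is mentioned only for confirming non-target progression.
- The formalin core in Section 9.1, which also goes for histopathologic review, is labelled with "initials, medical record number and the date of acquisition".
- Coded identifiers in Section 9.1 are there for confidentiality, not for a masked read.

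**The concern.** Grading dysplasia takes judgement, particularly at the P0/P1 boundary, where P0 already allows mild atypia and the plan prints no further criteria. A grader who knows that a slide is post-treatment may lean one way without intending to. With no control arm, such a lean cannot be told apart from a drug effect. The decision rests on whether 6 of 33 patients respond, so one or two cases tipped across the PR cut-off matter to the result. The 9.8% false-positive probability in Section 13 assumes that responses are counted without such error.

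**Working it through.** **Inputs.** The grid and cut-offs come from Section 11.1.4.1, and the decision rule and its error rates from Section 13. The drifted rates of 12.5% and 15% are assumptions, because the documents give no misreading rate.

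**1. Weight of histology.** The grid follows: site score = 2 + 10 × (size class − 1) + 2 × grade. Scores run from 2 (L1P0) to 28 (L3P3), a range of 26.
- Histology: 2 × 3 = 6 points, 6/26 = 23%.
- Size: 10 × 2 = 20 points, 20/26 = 77%.
- One grade is worth 2 points and one size step 10.

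**2. One grade milder, size unchanged, single site.** The fall is 2/score.

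| Baseline | Points | Fall | Call |
|---|---|---|---|
| L1P1 | 4 to 2 | 50.0% | PR |
| L1P2 | 6 to 4 | 33.3% | SD |
| L1P3 | 8 to 6 | 25.0% | SD |
| L2P1 to L2P3 | 14, 16, 18 | 14.3%, 12.5%, 11.1% | SD |
| L3P1 to L3P3 | 24, 26, 28 | 8.3%, 7.7%, 7.1% | SD |

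Only L1P1 becomes a response. With two or three sites, one grade at one site alone never reaches 40% (0 of 72 and 0 of 354 baseline combinations). If every dysplastic site is read one grade lower, 2 of 72 and 3 of 354 combinations reach PR, all with every lesion under 2 cm. These are unweighted grid cells, not expected shares of patients.

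**3. One grade together with a drop of one size class (L3 to L2).**
- L3P2, grade unchanged: (26 − 16)/26 = 38.5%, SD. One grade milder: (26 − 14)/26 = 46.2%, PR. The unchanged-grade case is the protocol's Patient B.
- L3P3, grade unchanged: (28 − 18)/28 = 35.7%, SD. One grade milder: (28 − 16)/28 = 42.9%, PR.
- Two L3P2 lesions, both dropping to L2: (52 − 32)/52 = 38.5%, SD. One grade milder at one of them: (52 − 30)/52 = 42.3%, PR.

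**4. The other direction.**
- L3P1 dropping to L2 is PR at (24 − 14)/24 = 41.7%. Read one grade worse it is (24 − 16)/24 = 33.3%, SD.
- With size unchanged, one grade worse is progression at a single L1 or L2 site (increases of 12.5% to 100%). At L3 it is not (7.7% to 9.1%).

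**5. The design.** P(positive) = Σ over x = 2 to 16 of Bin(x; 16, p) × P(at least 6 − x responses in the remaining 17).
- Reproduced at p = 0.10: 0.0979, against the stated 9.8%; early stopping 0.515, against 51.5%.
- Reproduced at p = 0.25: 0.843, against 84.3%.
- Illustration at p = 0.125: 0.209. Extra responders expected in 33: 33 × 0.025 = 0.8.
- Illustration at p = 0.15: 0.351. Extra responders expected in 33: 33 × 0.05 = 1.7.

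**The case against.** Much of the case on the other side stands.

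- **Weight.** Because histology is one of two components, a reader might infer that it makes up half of the score. It does not: it carries 23% of the range.
- **How often one grade decides.** With size unchanged, a single-site flip needs L1P1. Eligibility makes that uncommon: criterion 1 calls for multifocal or large lesions, criterion 2 is already P0, and criterion 3 requires moderate dysplasia. A lone L1P1 lesion fits essentially criterion 4. Elsewhere a size drop is needed as well. Patient B's lesion shrank from 4 cm to 2 cm, so that case is not a response made from nothing.
- **The label.** A reader might infer that the graded slides carry patient and date. The documents state that label for the research formalin core only. Section 9.1 has tissue for pathological assessment taken first and does not describe its label. The concern rests on the absence of any masking rule, not on the label.
- **The error rate.** A reader might infer that the 9.8% has been shown to fail. It has not. The 12.5% and 15% rates are not derived from any misreading rate or lesion mix, and misreading can cut both ways.
- **Size.** It is measured unmasked by ruler or photograph (Section 11.1.3) and moves 10 points at a step. Masking histology cannot protect that component.
- **Stakes.** A positive result leads only to consideration of further testing.

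These points limit the size of the problem. They do not supply a masked read, and they leave borderline cases that one grade decides.

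**Conclusion.** The concern holds in limited form. Dysplasia grade enters the primary endpoint of an open-label, single-arm trial, and no section masks the grader to time point or says who the grader is. One grade can tip a case over the 40% cut-off in small, mildly dysplastic lesions, and in L3P2 or L3P3 lesions that drop one size class. It can also take a response away.

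How often this would happen cannot be worked out from the documents, which give neither a misreading rate nor the baseline mix of size and grade. The rise from 9.8% to 20.9% or 35.1% is therefore conditional on an assumed net lift of 2.5 or 5 percentage points. It shows how sensitive the 6-of-33 rule is and does not predict what will happen. The change is worth making because it removes an avoidable source of bias from an uncontrolled count at small cost.

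**What to change.** In Sections 11 and 13, name the role that grades the study biopsies. State that, for the primary endpoint, this pathologist regrades the existing baseline and post-treatment H&E slides in random order, with patient identity and date covered. Do this once before the stage-1 decision and once before the final analysis. Use the masked grade in the composite score, and keep the real-time grade for patient care.

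The cost is about a paragraph of text and a re-read of at most about 33 patients × 3 sites × 2 times = 198 slides, a few hours of pathologist time. It needs no new biopsy and no additional reader. It does not address the unmasked size measurement, which carries most of the score, and the text should say so.

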11.1.1 Definitions

Evaluable for Target Disease response. Only those participants who have measurable disease present at baseline, have received at least one cycle of therapy, and have had their disease re-evaluated will be considered evaluable for target disease response. These participants will have their response classified according to the definitions stated below. (Note: Participants who exhibit objective disease progression prior to the end of cycle 1 will also be considered evaluable.)

Evaluable Non-Target Disease Response. Participants who have lesions present at baseline that are evaluable but do not meet the definitions of measurable disease, have received at least one cycle of therapy, and have had their disease re-evaluated will be considered evaluable for non-target disease. The response assessment is based on the presence, absence, or unequivocal progression of the lesions.

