3. PARTICIPANT SELECTION

Participants must meet the following eligibility criteria on screening examination to be eligible to participate in the study:

Eligibility Criteria

3.1.1 Subject must have have a confirmed diagnosis of high-risk oral leukoplakia which is defined by *any of the following*:

- (1) Diagnosis of oral PVL with multifocal lesions (≥ 2) or contiguous lesions ≥ 3 cm or a single lesion ≥ 4 cm in largest diameter (at least one lesion with any degree of dysplasia)
- (2) Diagnosis of oral PVL without dysplasia on biopsy but with 4 oral cavity quadrant involvement
- (3) Diagnosis of leukoplakia in at least 1 lesion with moderate dysplasia (without a diagnosis of oral PVL) for which surgery is indicated, but not feasible or patient refused.
- (4) Diagnosis of erythroplakia or erythroleukoplakia with any degree of dysplasia for which surgery is indicated, but not feasible or patient refused.

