11.1.2 Disease Parameters

Measurable disease. Measurable lesions are defined as those that can be accurately measured in at least one dimension (longest diameter to be recorded) as ≥ 10 mm by bidirectional measurements on oral examination. All lesion measurements must be recorded in millimeters (or decimal fractions of centimeters).

Non-measurable disease. All other lesions (or sites of leukoplakia), including small lesions (longest diameter < 10 mm), are considered non-measurable disease.

Target lesions. All measurable lesions up to a maximum of 3 lesions should be identified as **target lesions** and recorded and measured at baseline. Target lesions should be selected on the basis of their size (lesions with the longest diameter), be representative of the degree of high-risk oral leukoplakia, but in addition should be those that lend themselves to reproducible repeated measurements. It may be the case that, on occasion, the largest lesion does not lend itself to reproducible measurement in which circumstance the next largest lesion which can be measured reproducibly should be selected. A sum of the diameters (longest for all oral leukoplakia lesions) for all target lesions will be calculated and reported as the baseline sum diameters. The baseline sum diameters will be used as reference to further characterize any objective tumor regression in the measurable dimension of the disease.

Non-target lesions. All other lesions (or sites of leukoplakia) including any measurable lesions over and above the 3 target lesions should be identified as **non-target lesions** and should also be recorded at baseline. Measurements of these lesions are not required, but the presence, absence, or in rare cases unequivocal progression of each should be noted throughout follow-up.

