13. STATISTICAL CONSIDERATIONS

The primary objective of this trial is to evaluate best overall response rate (CR+PR). A two-stage design (Simon's optimal design) will be used to minimize the number of patients enrolled. Sixteen eligible patients who start protocol treatment are to be accrued in the first stage. If there are ≤ 1 patients with disease in response, accrual to this trial will be closed with the expectation that there is little evidence that the response rate will reach 25%. The probability that the trial will close early is 51.5% if the true response rate is 10%. If there are >1 patients with disease in response, accrual will continue until a total of 33 eligible patients who start protocol treatment are entered. If there are > 5 patients with disease in response among 33 eligible patients who began protocol treatment, further testing of this regimen will be considered. If the true response rate is 25%, the probability of concluding the regimen is effective is 84.3%, if the true response rate is 10%, the probability of concluding the regimen is effective is 9.8%. Allowing for patients to be declared ineligible or to not start protocol treatment after registration, a total of 35 patients will be entered.

The primary efficacy population includes all eligible patients who begin protocol treatment. Best overall response will be summarized as a proportion with a corresponding exact 95% confidence interval (CI) (if the trial closes to accrual after the first stage), or a corresponding 95% (two-stage) CI if the trial closes to accrual after the second stage.

For secondary objectives:

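### Measurable disease is not an entry criterion, yet a patient whose lesions are all under 10 mm counts in the CR+PR denominator and is scored in two conflicting ways

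*Combined protocol and SAP*

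**What the plan says.** **Entry (3.1.1).** Two of the PVL options carry a lesion size: contiguous lesions of at least 3 cm, or a single lesion of at least 4 cm. Multifocal PVL, four-quadrant PVL without dysplasia, erythroplakia or erythroleukoplakia, and the third route, "Diagnosis of leukoplakia in at least 1 lesion with moderate dysplasia", set no minimum size. Nothing in section 3 asks for measurable disease.

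**Measurability (11.1.2).** A measurable lesion has a longest diameter of at least 10 mm, while "small lesions (longest diameter < 10 mm), are considered non-measurable disease". Target lesions are picked from the measurable ones.

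**Response (11.1.1, 11.1.4).** Evaluability for target response is limited: "Only those participants who have measurable disease present at baseline, have received at least one cycle of therapy". The composite score and its PR band (a 40-80% fall) stand under the target-lesion heading, 11.1.4.1. Patients with only non-measurable lesions are judged on presence, absence or unequivocal progression. Their table in 11.1.4.4 offers CR, Non-CR/non-PD, not evaluated, or PD. It has no PR row.

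**Analysis (13).** The endpoint is best overall response, CR+PR. "The primary efficacy population includes all eligible patients who begin protocol treatment". The decision rule counts "patients with disease in response among 33 eligible patients who began protocol treatment".

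**The concern.** Sections 3.1.1, 11.1.1 and 13 describe different sets of patients. A patient can be eligible, be treated, count among the 16 or the 33, and yet have no route to PR under the non-measurable table.

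The grid in 11.1.4.1 points the other way. Step 1 grades each lesion, and class L1 covers anything under 2 cm with no lower limit, so an 8 mm lesion has a score. The primary objective in 1.2 also names both size and degree of dysplasia, whereas the non-measurable table uses neither.

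The same patient's primary endpoint can thus be read two ways. With cut-offs of more than 1 response in 16 and more than 5 in 33, reclassifying one patient can change either decision, so the rule should be settled before outcomes are known. A second question is which patients the 25% target describes, because patients with a lower chance of response pull the overall rate down against fixed cut-offs.

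**Working it through.** **1. Two readings of one patient.** Take an eligible patient with a single 8 mm lesion that goes from moderate dysplasia to keratosis without dysplasia and remains visible.
- Grid (11.1.4.1): L1P2 = 6 points falls to L1P0 = 2 points. (6 - 2)/6 = 66.7%, which lies in the 40-80% band: PR, a responder.
- Non-measurable table (11.1.1, 11.1.4.4): the lesion persists, so Non-CR/non-PD: a non-responder.

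**2. The plan's own figures.** Inputs from section 13: stage 1 n = 16, stop at 1 or fewer responses; total n = 33, success at 6 or more; rates 10% and 25%.
- Early stopping = (1-p)^16 + 16p(1-p)^15. At p = 0.10 this is 51.47% (stated 51.5%).
- Probability of success = sum over x = 2 to 16 of P[Bin(16,p) = x] × P[Bin(17,p) ≥ max(0, 6-x)]. At p = 0.10 this is 9.79% (stated 9.8%). At p = 0.25 it is 84.27% (stated 84.3%).

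All three reproduce.

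**3. Dilution, if 25% refers to measurable patients only.** Let f be the share of treated patients with only non-measurable lesions and q their CR rate. The documents give neither, so both are assumptions. The overall rate is p = 0.25(1-f) + qf, put through the same rule.

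| f | p, q = 0 | power, q = 0 | p, q = 10% | power, q = 10% |
|---|---|---|---|---|
| 0% | 25.00% | 84.3% | 25.00% | 84.3% |
| 5% | 23.75% | 80.3% | 24.25% | 82.0% |
| 10% | 22.50% | 75.6% | 23.50% | 79.4% |
| 15% | 21.25% | 70.2% | 22.75% | 76.6% |
| 20% | 20.00% | 64.1% | 22.00% | 73.5% |

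With q = 25%, p stays at 25% and power at 84.3% for every f. With q = 0, power drops below 80% once f exceeds about 5.3%.

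**4. As counts among 33** (allocated at random to the two stages): one such patient gives 82.1% with q = 0 and 82.9% with q = 10%. Two give 79.6% and 81.5%.

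**The case against.** A reader might infer that these patients cannot respond and that the stated power is not delivered. The documents support neither.

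- **CR remains open.** Section 11.1.4.2 defines CR for non-target lesions as visual disappearance for at least 4 weeks, and the non-measurable table carries it to an overall CR. The q = 0 column is therefore a worst case.
- **The 84.3% is conditional and correct.** It is stated for a true rate of 25%, in a section that counts all eligible treated patients. Read as written, the 25% already belongs to that population and there is no shortfall. A loss appears only if 25% was meant for measurable patients. Keeping lower-responding patients in the denominator does not raise the false-positive risk either.
- **The affected number is unknown.** Every lesion must be under 10 mm. Some PVL options require 3 cm or 4 cm, and section 9.1 asks for four research cores from the dominant lesion, which makes very small disease less likely, though it does not rule it out. The 5-20% range is illustrative.
- **PR in small lesions is arguable on the text.** Section 11.1 speaks of the change in size of each lesion, and Step 1 grades each one. The target-lesion heading and the table without a PR row weigh against that reading, but the documents do not settle it.

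The first three limit what can be said about power. The fourth confirms the conflict in the endpoint rather than removing it.

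**Conclusion.** The inconsistency is established from the text: no measurable-disease criterion at entry, PR tied to target lesions, an all-treated denominator, and a grid that would still score lesions under 10 mm. For a patient with only such lesions, the primary endpoint depends on which subsection is applied.

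The effect on power is conditional. It needs f above zero, the 25% to have been meant for measurable patients, and a CR rate below 25% in the others. On those terms a 10% share costs about 5 to 9 percentage points (84.3% to 79.4% or 75.6%), and a single patient among 33 costs 1 to 2. If f is zero, or if 25% describes all eligible treated patients, the stated 84.3% stands. This is worth correcting because the remedy is cheap, not because the design has been shown to be underpowered.

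**What to change.** Choose one rule and write it in before responses are assessed.

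1. **Entry criterion.** Add to 3.1.1 that at least one lesion must be measurable (10 mm or more). This is the cleaner option. It costs slightly fewer candidates, and the 33 and the cut-offs stay as they are.
2. **Scoring rule.** State in 11.1.4.1 that the composite is scored for every biopsied baseline site, including those under 10 mm (class L1), and amend 11.1.1, 11.1.2 and the non-measurable table in 11.1.4.4 to match. This needs several wording edits but does not affect accrual. It does not open PR to everyone: the lowest grid value is 2 points, so a site already at L1P0 has no lower class to move to. The text should say how such a site is handled.

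Under either option, add one sentence to section 13 saying that the 25% target is the rate among all eligible treated patients.
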